To determine the imaging characteristics of NETSPOT versus ¹⁸F FDG PET/CT in the setting of inflammation.

To determine if NETSPOT imaging uptake correlates with tumor HPV-positivity.

To determine if patients with tumor uptake on NETSPOT imaging exhibit different disease outcomes than patients without uptake.

Hypothesis:

List the clinical hypotheses in order of priority

NETSPOT imaging will be at least equivalent to ¹⁸F FDG PET/CT in the detection and staging of HNSCC.

The combination of NETSPOT imaging and ¹⁸F FDG PET/CT, will have increased specificity for detecting the primary site for HNSCC of unknown primary than ¹⁸F FDG PET/CT alone.

The combination of NETSPOT imaging and ¹⁸F FDG PET/CT, will have increased specificity for detecting disease recurrence and metastasis following treatment than ¹⁸F FDG PET/CT alone.

Is a study protocol already available (Yes/No)? If yes, please attach to the IIS form

No.

Study Design/Clinical Plan:

Provide a concise overview stating the type of experimental design (for ex, randomized/non-randomized, condensed eligibility criteria etc)

Design: This study will be designed as a “proof-of-concept” trial to compare NETSPOT with ¹⁸F FDG PET/CT for HNSCC.

Inclusion Criteria:

HNSCC patients undergoing planned ¹⁸F FDG PET/CT at time of primary diagnosis.

HNSCC patients undergoing planned ¹⁸F FDG PET/CT for unknown primary site.

HNSCC patients undergoing planned ¹⁸F FDG PET/CT after completion of adjuvant treatment.

Exclusion Criteria:

Inability to undergo ¹⁸F FDG PET/CT imaging due to medical comorbidities.

Enrollment:

Patients meeting inclusion criteria will be enrolled on evaluation. Based on our current clinical volume, we plan to enroll 30 patients over a 6 month time frame.

Preliminary analysis (outlined below) will be done after the first 30 patients to assess the utility of NETSPOT imaging in HNSCC.

Treatment:

List the clinical dosage/dosage form, route, and dose regimen

Brief Overview:

Patients meeting inclusion criteria will be consented at the time of scheduling.

All patients will undergo ¹⁸F FDG PET/CT per established protocol.

Following ¹⁸F FDG PET/CT, the patient will undergo NETSPOT imaging with the AAA-provided dose. These scans will be performed no less than 24 hours, no more than 7 days apart.

Analysis:

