Both ¹⁸F FDG PET/CT and NETSPOT images will be reviewed by the senior radiologist and the primary surgeon for concordance between images. SUV will be measured for both images and recorded.

Patients will undergo clinical follow-up based on ¹⁸F FDG PET/CT results as per protocol.

True positive results will be recorded for both ¹⁸F FDG PET/CT and NETSPOT images and analyzed for sensitivity and specificity.

For patients undergoing surgical treatment, pathology results including routinely reported HPV markers will be recorded and compared to NETSPOT imaging characteristics.

Follow-up

All enrolled patients will be followed for 1 year after imaging.

Expected Results/Outcomes:

We expect that ¹⁸F FDG PET/CT and NETSPOT will have similar uptake and specificity for primary tumor. We hypothesize that NETSPOT will have increased specificity for unknown primary site tumor and recurrent or metastatic disease. Finally, we hope that NETSPOT positivity in HNSCC will allow for future study of targeted radionuclide therapies for HNSCC.

Applicability of Results:

Any other information regarding the medical need and/or the strategic importance of the research which may help the committee's evaluation

A proof-of-concept trial to compare SSTR/ PET/CT with ¹⁸F FDG PET/CT in the head and neck cancer population would be a novel use of the NETSPOT technology. The study is warranted based on past data and the potential for success, especially in patients with oropharyngeal tumors, previous radiation or inflammatory disease; all of whom ¹⁸F FDG PET/CT is difficult to interpret. If the hypothesis is supported, Advanced Accelerator will have a new application for the NETSPOT technology and a new area for business development and revenue.

Additional Research (if applicable):

Histology, biomarkers, PK etc.

Statistical Plan:

Include justification for clinical sample size and primary hypothesis testing

Statistical Considerations:

The primary objective of this study is to evaluate SSTR receptor expression in the head and neck cancer population. The secondary objective is to assess the concordance based on SSTR PET/CT with and without FDG PET/CT outcomes.

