A Student t-test will be used to assess the difference of SSTR expression between the diagnostic results (positive vs negative) and Fisher's exact test will be used to assess the association between dichotomized expression (high vs low) and a binary outcome (positive vs negative). The sensitivity will be estimated by a proportion of true positives that are correctly identified by the new method. The specificity will be estimated by a proportion of true negative that are correctly identified by the new method. The corresponding 95% confidence intervals will be estimated based on binomial distributions.

Sample Size: Based on the two-sided t-test, a sample size of 30 will have 81% power to detect 0.95 standard deviations of the SSTR expression between positive and negative outcomes (15 per group) at a 0.10 significance level. In addition, based on the historical data and current literatures, head and neck squamous cell carcinoma (HNSCC) makes up 90% of head and neck cancers. For primary tumor detection, 18F FDG PET/CT is about 96% sensitive (oral cavity only) and anywhere from 91%-98% accurate at detecting lymph node metastasis, with sensitivity of 67%-79%, and specificity of 82-95%. For detecting recurrent disease, 18F FDG PET/CT is ranged from 83%-100% sensitive and 90-98% specific. Based on one-sided non-inferiority test for two correlated proportions with a concordance of 0.90, when the maximum allowable difference between these proportions that still results in non-inferiority (the range of non-inferiority) is 0.15, a sample size of 30 subjects achieves 81% power at a significance level of 0.10.

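### The only image read described is a joint review of both scans for concordance; nothing keeps the NETSPOT call independent of the FDG result or of the findings used to judge truth

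*Combined protocol and SAP*

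**What the plan says.** In the combined protocol and SAP, the Analysis list under Study Design/Clinical Plan states that the FDG PET/CT and NETSPOT "images will be reviewed by the senior radiologist and the primary surgeon for concordance between images". SUV is measured on both scans. True positives are then recorded for each scan and analysed for sensitivity and specificity.

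Under Brief Overview, every patient has FDG first and NETSPOT between 24 hours and 7 days later. The Analysis list bases clinical follow-up on the FDG result.

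These calls serve several aims:

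- The first-listed hypothesis is that "NETSPOT imaging will be at least equivalent to" FDG PET/CT in detection and staging.
- Expected Results/Outcomes adds: "We hypothesize that NETSPOT will have increased specificity for unknown primary site tumor and recurrent or metastatic disease".
- Statistical Considerations says: "The secondary objective is to assess the concordance based on SSTR PET/CT with and without FDG PET/CT outcomes". It also defines accuracy for NETSPOT alone: "The specificity will be estimated by a proportion of true negative that are correctly identified by the new method".
- The Sample Size paragraph sizes a paired comparison: "Based on one-sided non-inferiority test for two correlated proportions with a concordance of 0.90", with margin 0.15, 30 subjects, 81% power and a significance level of 0.10.

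No section states the order of reading, what the readers may see, whether any call is masked, or when the joint review takes place relative to pathology and the one-year follow-up.

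**The concern.** The aims need two different kinds of read. A joint review suits the concordance and combined-imaging objectives. An accuracy estimate for NETSPOT alone, and a paired comparison with FDG, need a NETSPOT call that does not depend on the FDG result or on the evidence used to decide who has disease. The plan describes only the first kind of read and then uses per-scan results for the second purpose.

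The route to dependence lies in the plan's own steps. FDG is already done when NETSPOT is read, FDG drives the work-up, one of the two reviewers is the treating surgeon, and the stated purpose of the review is to compare the scans. At stake are the first-priority hypothesis, the hypothesised specificity gain and the agreement result. The problem cannot be repaired at analysis, because an independent call that was never recorded cannot be recovered.

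**Working it through.** **1. The plan's own figure.** Inputs from the Sample Size paragraph: n = 30, concordance 0.90 (discordance 0.10), margin m = 0.15, one-sided α = 0.10 (z = 1.2816). The true difference is taken as zero, which the paragraph does not state. The check uses the score test for paired proportions.

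- With D = −0.15 and discordance split 0.05/0.05, the null-constrained cell q solves 2q² − 0.40q + 0.008625 = 0. So q = (0.40 + √(0.16 − 0.069))/4 = 0.1754.
- Null variance: 2q + D(1 − D) = 0.3508 − 0.1725 = 0.1783, SD 0.4223. SD under no difference: √0.10 = 0.3162.
- Power = Φ[(0.15 × √30 − 1.2816 × 0.4223)/0.3162] = Φ(0.887) = 81.2%.
- Exact enumeration of the same test gives 81.1%.

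The stated 81% reproduces and is not in dispute.

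**2. If calls are drawn toward FDG.** Among patients with disease (for sensitivity) or without it (for specificity), let b be the share positive on NETSPOT only and c the share positive on FDG only. Suppose a share s of each kind of discordant NETSPOT call is changed to match FDG.

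- Observed difference = (b − c)(1 − s).
- Observed discordance = (b + c)(1 − s).

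For any s above zero, concordance rises wherever there was discordance, and any difference moves toward zero. If NETSPOT is worse, it looks closer to FDG. If NETSPOT is better, part of the gain is lost.

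**3. If calls are drawn toward the truth.** Suppose instead that knowledge of pathology or follow-up corrects a share t of wrong NETSPOT calls. Accuracy A becomes A + t(1 − A), which is never lower than A. Concordance rises where FDG was right and NETSPOT wrong, and falls where both were wrong. So NETSPOT is flattered, and agreement can move either way.

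Both mechanisms can act in the same study, so the sign of the net effect is not determined.

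**4. What the documents allow on size.** They give neither s nor t. They do give two bounds.

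- Since |b − c| cannot exceed b + c, a concordance of 0.90 in the group analysed limits the true difference to 10 points.
- The Sample Size paragraph puts FDG specificity for recurrent disease at 90–98%, so the largest possible NETSPOT gain there is 2 to 10 points. With an assumed s of 0.10, step 2 hides 0.2 to 1.0 point; with s = 0.25, 0.5 to 2.5 points.

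These values of s are illustrations, not estimates.

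**5. Power if independent reading lowers agreement.** Same exact test, n = 30, no true difference:

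| Concordance | Power |
|---|---|
| 0.90 (plan) | 81.1% |
| 0.85 (assumed) | 73.8% |
| 0.80 (assumed) | 67.0% |

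**The case against.** **This is a proposal form, and reading rules belong in the later protocol.** The form says that no study protocol exists yet and asks only for a concise overview. This lowers the gravity of the gap but does not close it. The form does state a read, and that read is unsuited to one of its two uses; the text also commits to a margin, a significance level and a power.

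**A separate result per scan is already implied.** This stands. SUV and true positives are recorded for both scans, and an FDG interpretation must exist, because it directs follow-up. It would be wrong to infer that the plan has no per-scan call. What is missing is how the NETSPOT call is made and what the reader knows at that point.

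**The plan does not say the reads are unmasked.** This also stands. A reader might infer a side-by-side, unmasked reading; the documents are silent. The point is that such a reading would comply with the text.

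**SUV is a measurement and needs no masking.** No SUV cut-off for a positive call is given, so the call remains a judgement.

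**The effect may be small against sampling error in 30 patients.** This is possible, and the bounds in step 4 of the working are consistent with it. However, a larger sample would not remove a systematic dependence between the calls.

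**Withholding all clinical information would be artificial.** This is accepted. Post-treatment patients are eligible, and treatment history may be needed to interpret uptake. The independence required is from the other scan and from the evidence used to judge truth.

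**Conclusion.** The point holds as a gap in the reading design. As written, the NETSPOT calls behind sensitivity, specificity and the paired non-inferiority comparison can depend on the FDG result and on pathology or follow-up, and no step prevents it.

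A reader might go further and conclude that the design is biased in favour of equivalence. The documents do not support that. Pull toward FDG favours equivalence only if NETSPOT is truly worse, and it hides a gain if NETSPOT is better. Knowledge of the truth would flatter NETSPOT whichever scan is better. The net direction is unknown, and no size can be drawn from the documents. The plan's 81% power is correct on its stated inputs, taking no true difference.

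The change should be made before any scan is read. Confidence is medium: the silence of the text is certain, but how the team would actually read the scans is not.

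**What to change.** Write the following into the protocol.

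- Before the joint review, the existing senior radiologist records and locks a positive/negative call and SUV for NETSPOT, masked to the FDG scan and report, pathology and HPV results, and follow-up.
- A separate FDG call is recorded and locked without access to NETSPOT.
- Basic indication and treatment history may stay available to the reader if this is stated in advance and is the same for both scans.
- Sensitivity, specificity and the paired comparison use only the locked calls.
- The radiologist–surgeon review follows, and serves the concordance-review and combined-imaging objectives.
- Clinical FDG reporting and care are unchanged.

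**Cost.** Extra reading time for 30 patients by an existing reader: 30 × 2 = 60 separate reads. If the same radiologist made the clinical FDG read, some recall will remain. Observed concordance may fall below the assumed 0.90, with the loss of power shown in step 5 of the working; the sponsor should accept that loss knowingly.

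Masking does not settle the positivity criterion, the unit of analysis or the reference standard. These also need stating before the locked calls are scored.

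### Follow-up is driven by FDG PET/CT and nothing independent of the scans decides disease status, so NETSPOT-only findings are less likely to be verified and the accuracy comparison is exposed to partial-verification bias

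*Combined protocol and SAP*

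**What the plan says.** The Analysis section of the combined protocol and SAP sets the basis for follow-up: "Patients will undergo clinical follow-up based on ¹⁸F FDG PET/CT results as per protocol". It then says "True positive results will be recorded for both ¹⁸F FDG PET/CT and NETSPOT images and analyzed for sensitivity and specificity".

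Two sources of information on disease status exist besides the scans:
- For patients who have surgery, "pathology results including routinely reported HPV markers will be recorded and compared to NETSPOT imaging characteristics".
- Under Follow-up, "All enrolled patients will be followed for 1 year after imaging".

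Both sets of images "will be reviewed by the senior radiologist and the primary surgeon for concordance between images". The first hypothesis is that "NETSPOT imaging will be at least equivalent to ¹⁸F FDG PET/CT in the detection and staging of HNSCC". Hypotheses 2 and 3 claim better specificity for the two scans combined than for FDG alone, in unknown-primary disease and in recurrence or metastasis after treatment.

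Statistical Considerations defines sensitivity and specificity through true positives and true negatives. Sample Size powers a one-sided non-inferiority test of two correlated proportions: concordance 0.90, margin 0.15, 30 subjects, significance level 0.10, power 81%.

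**The concern.** No section says what makes a result true. Pathology is assigned to comparison with NETSPOT characteristics, and the 1-year follow-up has no stated role in scoring. The only process tied to a scan result is follow-up, and it is tied to the comparator scan. The reference in that sentence to a protocol does not fill the gap, because the form states that no study protocol was yet available.

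An FDG-positive site therefore has a route to confirmation that a NETSPOT-only site lacks. What follows depends on how unverified sites are scored, which the plan leaves open:
- **Dropped.** Disease that FDG missed leaves the denominator. FDG's apparent sensitivity rises and NETSPOT-only detections are lost. This bears on hypothesis 1.
- **Counted as disease-free.** Sensitivity tilts in the same way. In addition, true NETSPOT-only lesions are scored as NETSPOT false positives and credited to FDG as true negatives. This bears on the specificity claims in hypotheses 2 and 3, to the extent that the combined reading calls such a site positive. It also bears on the higher specificity for NETSPOT itself anticipated under Expected Results.

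The study is justified by settings where FDG is hard to interpret, so discordant findings are central to its purpose.

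**Working it through.** **1. The plan's own figure.** Inputs from Sample Size: N = 30, margin 0.15, one-sided level 0.10, concordance 0.90. With no true difference, the discordance of 0.10 splits into NETSPOT-only p10 = 0.05 and FDG-only p01 = 0.05. The score test for paired proportions with restricted maximum-likelihood variance, enumerated exactly, gives power 0.811. The stated 81% is reproduced.

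**2. Assumptions for the illustration.** None of these is stated in the plan:
- The two correlated proportions are sensitivities.
- There are 30 diseased cases.
- Both scans have true sensitivity S = 0.79, the top of the nodal range quoted under Sample Size.
- All FDG-positive disease is confirmed, but only a share v of FDG-negative disease. The documents give no value for v, so a range is shown.
- Unconfirmed cases drop out.

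**3. Formulas.**
- Share confirmed: den = S + v(1 − S)
- Apparent FDG sensitivity: S / den
- Apparent NETSPOT sensitivity: (S − p01 + v·p10) / den
- Apparent deficit of NETSPOT: p01(1 − v) / den, since p10 = p01
- Power: the same score test with p01/den and v·p10/den, averaged over a confirmed number distributed Binomial(30, den)

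For v = 0.5: den = 0.79 + 0.5 × 0.21 = 0.895; FDG 0.79/0.895 = 88.3%; NETSPOT (0.74 + 0.025)/0.895 = 85.5%; deficit 0.025/0.895 = 2.8 points.

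| v | den | Apparent FDG | Apparent NETSPOT | Deficit (points) | Power |
|---|---|---|---|---|---|
| 1 | 1.000 | 79.0% | 79.0% | 0 | 81% |
| 0.9 | 0.979 | 80.7% | 80.2% | 0.5 | 79% |
| 0.75 | 0.9475 | 83.4% | 82.1% | 1.3 | 76% |
| 0.5 | 0.895 | 88.3% | 85.5% | 2.8 | 69% |
| 0 (limiting case) | 0.790 | 100% | 93.7% | 6.3 | 52% |

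**4. Dependence on S.** At v = 0.9, 0.75 and 0.5, power is 79%, 75% and 66% for S = 0.67 (bottom of the nodal range), and 79%, 76% and 70% for S = 0.83 (bottom of the recurrence range). The 96% quoted for primary tumours is not used, because a known primary is confirmed whatever FDG shows.

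**5. Direction of the error.** Keep FDG sensitivity at 0.79 and assume a true NETSPOT deficit equal to the margin (p01 = 0.20, p10 = 0.05, so 0.15). The chance of wrongly declaring non-inferiority is 9.2% at v = 1, 6.4% at v = 0.75 and 3.8% at v = 0.5. Under this model, incomplete verification makes a false claim less likely and a missed signal more likely.

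**6. The other scoring.** With p10 = 0.05, 30 diseased cases yield 30 × 0.05 = 1.5 expected NETSPOT-only lesions. At v = 0.5, 0.75 of these would become NETSPOT false positives if unverified sites count as disease-free. The effect on specificity cannot be computed, because the number of disease-free sites is not given.

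**The case against.** The strongest reply has four parts.

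**The proportions may not be sensitivities.** The plan never calls them that, and its Statistical Considerations put receptor expression and concordance first. Agreement between scans needs no reference standard. This stands: if the test compares positivity rates, the 81% is untouched. The planned sensitivity and specificity estimates, and hypotheses 1 to 3, still need a defined truth.

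**The effect is modest and conservative.** With at least half of FDG-negative disease confirmed, the deficit is at most 2.8 points at 79% sensitivity, against a margin of 15. This stands for the drop-out model. It says nothing about specificity if unverified sites are counted as disease-free.

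**This is a short proposal for a proof-of-concept study, and pathology and 1-year follow-up are already in it.** That makes the remedy cheap. It does not supply the missing assignment of those data to disease status.

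**A status rule may not raise v.** If work-up still follows FDG, a NETSPOT-only node may never declare its status within the year. This stands and limits what the fix can promise.

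Some stronger readings are tempting but not supported:
- A reader might infer that only true positives will be recorded, so that specificity cannot be estimated. The same sentence goes on to specificity, and Statistical Considerations defines it through true negatives, so negatives must be recorded too.
- A reader might infer that the joint review replaces a separate call for each scan. The text does not say so; it leaves open only whether the separate calls come first.
- Enrolment includes "HNSCC patients undergoing planned ¹⁸F FDG PET/CT after completion of adjuvant treatment", so fewer than 30 patients may have disease. With an assumed 20 diseased cases, power at 79% sensitivity is 65% even with full confirmation. That fall comes from case mix. Only the further fall, to 52% at v = 0.5, comes from verification.

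**Conclusion.** The concern holds as a design gap. Follow-up tied to the comparator scan, with no scan-independent rule for disease status, means that FDG-positive and NETSPOT-only findings would be verified differently. It affects nodal, recurrent, distant and unknown-primary sites. It does not affect known primaries or the concordance analysis.

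The power calculation itself is not in error; it makes no allowance for incomplete verification. Under the stated assumptions the loss is small if most FDG-negative disease is confirmed and material at half or less. The case v = 0 is a limit and is unlikely, given pathology and 1-year follow-up. A reader might infer a risk of a false non-inferiority claim; in the model examined the risk is the opposite one, a missed signal. This should be fixed before the accuracy results are relied on. Confidence in its size is medium, because v is unknown.

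**What to change.** Leave clinical management unchanged, and add the following:

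1. Set disease status by site or region (primary, nodal, distant or recurrent) with one rule: pathology where taken, otherwise the planned 1-year follow-up, applied whichever scan was positive.
2. Report how many sites remain undetermined, by scan result, and bound sensitivity and specificity with those sites counted both ways.
3. Record true and false positives and true and false negatives for both scans at that level, with confidence intervals that allow for several regions per patient.
4. Report final accuracy after the 1-year follow-up. The plan already says "Preliminary analysis (outlined below) will be done after the first 30 patients", so that analysis can stay as the preliminary one.
5. Have the existing readers log each scan's call before the joint concordance review.

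The cost is a short rule, a change to the data form and an extra recording step. No scan, biopsy or visit is added. The final accuracy result comes later, after the last patient's 1-year follow-up. Status based on follow-up is less certain than pathology and remains partly shaped by FDG-driven care. The rule therefore exposes and bounds the verification bias rather than removing it, and the report should state this as a limitation.

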Interestingly, HNSCCs have been found to express somatostatin receptors (SSTRs). SSTRs have also been found in laryngeal cancer specimens and cancers of the oral cavity and oropharynx, but not in control tissue^{1,2}. Recent studies have found that HPV causes mutations in the same pathways that activate SSTR expression on tumor cells³. These studies suggest a correlation with HPV-positive HNSCC and SSTR expression. This latter group of patients often have non-detectable primary tumors that arise from the oropharynx, an area that normally exhibits ¹⁸F FDG PET/CT uptake thus making tumor localization difficult. Schartinger et al studied SSTR PET/CT in a small series of HNSCC patients and found that all patients showed radionucleotide uptake on imaging⁴. Multiple case reports have been published showing similar uptake for head and neck squamous cell carcinomas by ⁶⁸Ga^{5,6}. An unpublished trial was performed comparing SSTR PET/CT with ¹⁸F FDG PET/CT for 35 patients with HNSCC; the study concluded that SSTR PET/CT had the potential to be more specific for HNSCC than ¹⁸F FDG PET/CT⁷. Unfortunately the study was small, HPV status was not correlated, and recurrent/post-treatment patients were not studied. These studies show that SSTR-specific imaging, such as NETSPOT, has the potential to be equal to and possibly more specific than ¹⁸F FDG PET/CT for HNSCC patients, especially in the setting of HPV positivity, unknown primary site tumors, and post-treatment follow-up. More importantly, a therapeutic target for SSTRs is widely available; as such, HNSCC patients who show clinical uptake on NETSPOT imaging may be candidates for future studies using targeted therapeutics.

Objectives and study aims:

List the primary/secondary objectives to correspond directly with the listed hypotheses; define the role of AAA compounds

Study Aim:

Evaluate utility of NETSPOT imaging for disease detection in HNSCC, as well as the potential for targeted receptor-specific therapeutics.

Primary Objectives:

To determine the utility of NETSPOT imaging, as compared to ¹⁸F FDG PET/CT, in detection and staging of HNSCC.

To evaluate the potential of NETSPOT imaging in guiding the use of targeted radiopeptides for HNSCC treatment.

Secondary Objectives:

To determine if NETSPOT imaging and ¹⁸F FDG PET/CT, when used together, can lead to improved tumor delineation and detection of metastatic disease.

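### HPV status is to be recorded only for surgical patients, although the HPV objective has no treatment limit, so the comparison may lose precision and reach

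*Combined protocol and SAP*

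**What the plan says.** The Secondary Objectives include "To determine if NETSPOT imaging uptake correlates with tumor HPV-positivity". No treatment subgroup is named.

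The Inclusion Criteria admit three groups: "HNSCC patients undergoing planned ¹⁸F FDG PET/CT at time of primary diagnosis", those having "FDG PET/CT for unknown primary site", and those having "FDG PET/CT after completion of adjuvant treatment". Surgery is not a condition of entry for any of them. The single exclusion criterion concerns ability to undergo the FDG scan.

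In the Analysis section, uptake is collected without a surgical limit: "SUV will be measured for both images and recorded". HPV is handled once, in the same section: "For patients undergoing surgical treatment, pathology results including routinely reported HPV markers will be recorded and compared to NETSPOT imaging characteristics". HPV is not an eligibility or baseline item. The Statistical Plan names no HPV test, population or sample size.

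HPV matters to the rationale. The Background faults an earlier 35-patient trial in these words: "Unfortunately the study was small, HPV status was not correlated, and recurrent/post-treatment patients were not studied". Of HPV-positive disease it says "This latter group of patients often have non-detectable primary tumors that arise from the oropharynx".

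**The concern.** A correlation between uptake and HPV status needs both values for each patient. The plan collects uptake for everyone but states a route to HPV status only for those who have surgery. Two things are at stake for this objective.

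- **Precision.** In a study of 30, each patient without an HPV result matters.
- **Reach.** Whether a patient enters the comparison depends on treatment. If treatment follows tumor site or stage, the result may not carry over to the non-surgical patients who were also enrolled. The Background ties HPV-positive disease to primaries that are hard to find, and unknown primary is one of the three inclusion groups. Surgical share, and so HPV ascertainment, could therefore differ between the groups.

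**Working it through.** **Step 1: set the rules side by side.**

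| Item | Who is covered |
|---|---|
| HPV objective | no treatment limit |
| Eligibility | three groups, surgery not required |
| SUV measurement | no treatment limit |
| HPV recording | patients undergoing surgical treatment |

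Only the last row is restricted. Nothing in the Statistical Plan fills the gap.

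**Step 2: reproduce the plan's own figure.** The Sample Size paragraph gives 81% power for 0.95 SD, 15 per group, two-sided t-test, alpha 0.10. The noncentral t distribution has 28 degrees of freedom and noncentrality 0.95 × √(15 × 15 / 30) = 2.60. It gives 81.4%, so the figure reproduces. It concerns SSTR expression by positive or negative outcome, not by HPV, and serves below only as a yardstick.

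**Step 3: illustrate the possible loss.** The document gives no surgical share, so the shares here are assumptions. So are a near-even HPV split, an HPV result for every surgical patient, and uptake analyzed as a difference in means. The 95% half-width in SD units is t(0.975, n1+n2−2) × √(1/n1 + 1/n2). For 15/15 that is 2.048 × 0.365 = 0.748.

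| Assumed surgical share of 30 | Patients with HPV status | Split | 95% half-width (SD) | Power for 0.95 SD, alpha 0.10 |
|---|---|---|---|---|
| 100% | 30 | 15/15 | 0.748 | 81.4% |
| 80% | 24 | 12/12 | 0.847 | 72.9% |
| 67% | 20 | 10/10 | 0.940 | 65.5% |
| 50% | 15 | 8/7 | 1.118 | 53.8% |
| 33% | 10 | 5/5 | 1.458 | 39.5% |

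Thirty is a ceiling, since some post-treatment patients may have no tumor at imaging. If 24 patients had tumor, surgical shares of 100%, 75%, 50% and 25% would leave 24, 18, 12 and 6 patients, with half-widths 0.847, 0.999, 1.286 and 2.267 SD.

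**Step 4: what selection on HPV status does.** HPV status is the grouping variable. If surgery were more common in one HPV group, the group sizes would change, but that alone would not shift the difference in mean uptake. Take 12 patients with a result: a 3/9 split gives 2.228 × √(1/3 + 1/9) = 1.485 SD, against 1.286 SD for 6/6. This is a loss of precision. Bias would need surgery to be related to uptake within HPV groups, and the document does not establish that.

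**Step 5: what wider recording could recover.** Suppose one third of 30 have surgery and existing reports supply HPV for half of the other 20. Then 10 + 10 = 20 patients have a result, and the half-width falls from 1.458 to 0.940 SD. If existing reports supply none, it stays at 1.458.

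**The case against.** The rule says what will be done for surgical patients; it does not forbid HPV results from biopsy or earlier pathology for the others. That is correct. A reader might infer that non-surgical patients are excluded from the HPV comparison, but the text supports only the narrower statement that no route is given for them.

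A reader might also infer that the HPV-uptake difference will be biased because surgery selects on HPV status. Step 4 shows why this does not follow. The Analysis section also bases clinical follow-up on the FDG result, so the document does not have NETSPOT uptake directing treatment. An indirect link through site or stage is possible but not shown.

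The loss may be small or nil. Every patient may have surgery, and an earlier resection may count for the post-adjuvant group. Review of the images by the primary surgeon suggests a surgical setting. All this stands as a limit on size, but none of it makes surgery a condition of entry, and the opening words of the rule allow that some patients will not have it.

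Finally, the document is a proposal form that states no separate protocol yet exists, and HPV sources could be settled later. That lowers the weight of the point. Still, the form goes beyond silence: it states a rule, and that rule is narrower than the objective it serves.

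On the remedy, surgical specimens may match the imaged lesion better than older tissue. This is a fair reason to show them separately.

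**Conclusion.** The mismatch is real: an objective without a treatment limit is served by an HPV rule limited to surgical patients. The consequence is a possible loss of precision and generalisability for one secondary objective. The primary objectives and the stated 81% power are not affected.

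The size cannot be derived from the document. It is zero if all patients have surgery. Under the assumptions in Step 3, the half-width grows from 0.748 SD with 30 patients to 1.118 SD with 15 and 1.458 SD with 10. These figures show the scale of the risk and do not predict the loss. The point is a cheap improvement to make before data forms are set, not a flaw that undermines the study.

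**What to change.** Replace the HPV sentence in the Analysis section with wording such as:

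> *Tumor HPV status will be taken from any existing pathology report (biopsy, nodal tissue, earlier resection or surgical specimen) for every enrolled patient, with source and date, and compared with NETSPOT imaging characteristics. The comparison will be repeated in patients whose result comes from a surgical specimen, as a sensitivity analysis. The number of patients without an HPV result will be reported by inclusion group.*

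If the investigators want surgical tissue only, the alternative is to limit the secondary objective to surgically treated patients. That makes the text consistent but recovers no data.

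The cost is extra chart abstraction, with no new procedure. Some results will still be missing, because the document does not say that biopsy or nodal reports include HPV. Some tissue will predate or differ from the imaged lesion, hence the source, the date and the sensitivity analysis. If existing reports add nothing, precision does not improve, but the missing results are at least counted.
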